5.1.3 Determination of “At Risk” of Severe COVID-19

Prior to randomization, the medical history of the participant will be reviewed. In Phases 2, 3a, Phase 3b and 3c, participants identified as being either 60 years of age or older OR who have

any of the medical conditions provided in [Appendix 5](#) will be categorized as “at risk” of severe COVID-19

Each of the medical conditions provided in [Appendix 5](#) is currently regarded as a known or suspected medical condition affiliated with risk of severe COVID-19 ([CDC 2021](#)).

At time of randomization, participants in Phases 2, 3a, 3b and 3c will be stratified by age (< 60 or \geq 60 years of age) and for participants < 60 years of age by risk of severe COVID-19; a total of 3 stratification factors.

5.1.4 Screen Failures

Screen failures are individuals who fail to meet all inclusion criteria or who meet at least 1 of the exclusion criteria. Rescreening will not be permitted but enrollment may be delayed if the entry criterion is specific to a time window; see Section [5.2.1](#). Reasons for screen failure will be collected and entered in the electronic data capture (EDC) system.

5.1.5 Swithcover/Further Study Vaccine Eligibility Criteria

At Day 92, all participants in Phase 1, 2, 3a and 3b will be reviewed for eligibility to receive further study vaccine based on meeting any of the following exclusionary criteria on Day 92. Participants meeting any of the following criteria will be excluded from receiving further study vaccine administration:

- Significant infection or other acute illness, including body temperature $>100.4^{\circ}\text{F}$ ($>38.0^{\circ}\text{C}$) on the day prior to or day of planned Swithcover/Further Study Vaccine vaccine administration (see Section [5.2.1](#)).
- Pregnant or breastfeeding.
- Persistence of symptoms from COVID-19 disease (recovered COVID-19, asymptomatic SARS-CoV-2 infection and/or nucleocapsid positive test is not exclusionary).
- Receipt of an off-study COVID-19 vaccine since study enrollment.
- Demonstrated inability to comply with the study procedures since study enrollment.
- Development of new severe allergy to vaccine components since study enrollment. See the IB for list of vaccine components.
- New onset of bleeding disorder considered a contraindication to IM injection or phlebotomy.
- New onset of immunosuppressive or immunodeficient state, asplenia, or recurrent severe infections.
- Has received a live replicating vaccine within 28 days prior to intended Swithcover/Further Study Vaccine vaccine administration or an inactivated or non-replicating vaccine within 14 days prior to intended Swithcover/Further Study Vaccine vaccine administration. Please see Section [5.2.1](#) for guidance on deferral of study vaccination.

- Has received immunosuppressive therapy, including cytotoxic agents or has initiated systemic corticosteroid therapy. If systemic corticosteroids have been administered short term (<14 days) for treatment of an acute illness, see Section 5.2.1 for additional guidance. Inhaled/nebulized, intra-articular, intrabursal, or topical (skin or eyes) corticosteroids are permitted.
- Has received systemic immunoglobulins or blood products within the past 3 months.
- Has newly identified that they are investigator site staff members, employees of the Sponsor or the CRO directly involved in the conduct of the study, or site staff members otherwise supervised by the investigator or immediate family members of any of the previously mentioned individuals.
- Has a clinically significant acute or chronic medical condition or physical examination findings for which, in the opinion of the investigator, further study vaccine administration would not be in the best interest of the participant (eg, compromise the well-being) or that could prevent, limit, or confound the protocol-specified assessments.

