2.8 Risk: Benefit Assessment

2.8.1 Potential Risks

Detailed information about the known and expected benefits and risks and reasonably expected AEs of the LUNAR COVID-19 vaccines is provided in the IB. The expected benefits and risks of ChAdOx1 are summarized in the approved label for this vaccine. This reference material is

provided separately. In addition to the risk mitigation measures incorporated into the study design, a summary of the potential risks of treatment with the LUNAR COVID-19 vaccines, together with potential mitigation for these risks, is shown in [Table 1](#).

Table 1 Risk Minimization Measures Included in Clinical Trials of LUNAR COVID-19 Vaccines

Risk	Mitigation
Local and Systemic Reactogenicity	
• Vaccination via the intramuscular route results in a lower rate of local reactions than intradermal (I.D.) or subcutaneous (S.C.) injection (Zhang 2015).• Local injection site reactions and systemic AEs such as headache, fever, myalgia, or arthralgia may be treated with acetaminophen (paracetamol), ibuprofen, or other non-steroidal anti-inflammatory drugs and/or with topical agents (eg, ice or heat); however, administration of these agents within 24 hours prior to study vaccine administration is prohibited. Allergic AEs may be treated with corticosteroids or H1/H2 blockers as indicated and if not otherwise contraindicated.• For anaphylaxis or immediate type hypersensitivity (≤ 4 hours after injection) of at least moderate severity following the administration of the study vaccine, subsequent doses of study vaccine will not be administered.
VAERD if subsequently infected with SARS-CoV-2	
• Risk minimization measures to date have included ongoing characterization of the immune responses in nonclinical and clinical studies. These demonstrate that vaccination with ARCT-021 leads to reduction in viral replication (NHP and mouse data), protection from COVID-19 disease (NHP and mouse data), no evidence of lung injury (NHP data), and Th1-biased immune response (mouse and human data).• In this study, an independent DSMB or other safety committee will assess all cases of severe COVID-19 for imbalance in order to assess the risk of VAERD. The DSMB will make recommendations concerning modifying or stopping the study in order to manage any risk(s) identified

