Phase 1 participants must be <60 years of age. Phase 2, 3a, 3b and 3c participants will include elderly (≥ 60 years) participants as well. Phase 3b and Phase 3c will enrich for participants at higher risk for COVID-19 by attempting to enroll individuals considered at high risk due to their workplace environment or living conditions.

For Phases 2, 3a, 3b and 3c, after a 10-day Screening period, prior to randomization, participants will be stratified by age (< 60 or ≥ 60 years of age) and for participants < 60 years of age by risk of severe COVID-19. Participants will be defined as “at risk” if they are 60 years of age or older OR have medical history described as putting the individual at risk or possibly at risk of severe coronavirus disease 2019 (COVID-19) ([Appendix 5](#)). As the eligibility criteria for Phase 1 exclude participants ≥ 60 years of age or otherwise at risk for severe COVID-19, stratification will not occur for Phase 1.

Participants in all study phases will undergo informed consent and screening procedures prior to enrollment. After enrollment, participants will be randomized to groups. Study vaccines will be given in a supervised medical setting. All participants will be evaluated for reactogenicity (solicited adverse events) and reporting of unsolicited adverse events and concomitant medications through a series of clinic visits and phone calls. Depending on the study phase, blood sampling for immunogenicity and testing for COVID-19 may be performed. See [Appendix 1](#) for an overview of study visits by study phase.

For participants in Phase 1/2/3a/3b, at the Day 92 visit and prior to receipt of further study vaccine, participants will be evaluated by the Investigator according to Further Study Vaccine eligibility criteria (Section [5.1.5](#)). Any participant who does not meet these criteria will not receive further vaccinations with study vaccine and will be asked to continue in the study through Final Visit (Day 394).

For participants that receive further doses of Study Vaccine at Day 92 and Day 120, this will occur in a blinded fashion in that participants and blinded site and Sponsor personnel will remain blinded to treatment assignment until End of Study (EOS).

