5.2.2 Discontinuation of Study Vaccine (Participant)

A participant may not receive additional study vaccine administrations for any of the reasons outlined in Section [5.1.5](#).

Additional reasons for discontinuation of study vaccine for a participant would include:

- Participant request to discontinue study vaccinations.
- Participant is lost to follow-up.
- New information becomes available that makes further participation unsafe.
- Termination of the trial study vaccinations.

Should study vaccine administration be discontinued, the participant will be encouraged to continue study participation for study evaluations through Day 394 (Final Visit).

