6 STUDY TREATMENTS

6.1 Method of Assigning Participants to Study Groups

Assignment of participants to Study Groups will proceed using an IRT system. The site personnel (study coordinator or specified designee) will be required to enter or select information including but not limited to the password, the protocol number, participant age and the participant code (a unique number identifying the participant), and participant's relevant underlying health conditions that will be used to determine "at risk" status prior to randomization. The site personnel will then be provided with a vaccine assignment. The IRT system will provide an unblinded confirmation report containing the participant code and study intervention allocation assigned. The confirmation report must be stored in the site's unblinded files away from the view of blinded site staff.

Participants will then be randomly assigned and stratified as described in Section 4.5.2. Treatment designation will be assigned in the IRT.

Confirmation of a participant's eligibility to receive additional study vaccine must be entered into the IRT prior to dispensing the assigned vaccination on Day 92.

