7.4.1.2.1 Assessment of Severity

The severity, or intensity, of an AE refers to the extent to which an AE affects the participant's daily activities. Changes in the severity of an AE should be documented to allow an assessment of the duration of the event at each level of intensity. AEs characterized as intermittent do not require documentation of onset and duration of each episode.

Unsolicited AEs: The intensity of unsolicited AEs will be rated as mild, moderate, or severe using the following criteria:

Mild:	These events require minimal or no treatment and do not interfere with the participant's daily activities. OR An event usually transient in nature and generally not interfering with normal activities.
Moderate:	These events result in a low level of inconvenience or concern with the therapeutic measures. Moderate events may cause some interference with normal functioning. OR An AE that is sufficiently discomforting to interfere with normal activities.
Severe:	These events interrupt a participant's usual daily activity and may require systemic drug therapy or other treatment. Severe events are usually incapacitating. OR An AE that is incapacitating and prevents normal activities.

Solicited AEs: The intensity of solicited AEs will be graded for severity as Grade 0, Grade 1 (mild), Grade 2 (moderate), Grade 3 (severe), or Grade 4 (potentially life threatening). Further details on the toxicity grading scales are provided in [Appendix 4](#).

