- f Collection of blood samples is outlined in Section 4.5.5.3. Phase 1, Phase 2 and Phase 3a participants (the Immunogenicity Subgroup) will have blood collected more frequently for assessment of antibody responses to the SARS-CoV-2 spike protein. These blood samples will be sent to the central laboratory.
- g Collection of nasal swab samples is outlined in Section 4.5.5.3. Use of provided nasal swab test kits (including 2 collection containers) to be sent to the central laboratory is strongly preferred. Approved alternate measures of virological confirmation of SARS-CoV-2 may be performed if use of provided kits is not feasible. Note: For Phase 1/2/3a/3b, nasal swabs for RT-PCR test do not need to be performed after Day 92.
- h Confirm Switchover/Further Study Vaccine eligibility criteria (Section 5.1.5) prior to Switchover/Further Study Vaccine vaccine administration.
- i Study vaccine will be administered by intramuscular injection into the lateral aspect of the deltoid muscle of the nondominant arm. Study vaccine will be administered in an observer-blind fashion at Day 92 and Day 120 (if the participant meets eligibility criteria for Switchover/Further Study Vaccine). For participants who do not meet eligibility criteria for Switchover/Further Study Vaccine, study vaccination will not be performed.
- j For Switchover vaccinations, participants in Phase 1 and Phase 3b will be observed for at least 15 minutes and until clinically stable. Participants in Phase 2 and 3a will be observed for at least 30 minutes and until clinically stable for vaccinations 1, 2, and 3 (Day 92) and for at least 15 minutes and until clinically stable for vaccination 4 (Day 120).
- k Review of COVID-19 symptoms and risks will include a scripted interview of the participant for risks of recent exposure to COVID-19 and for symptoms of COVID-19 (Appendix 2). If symptoms or risk of COVID-19 is confirmed, testing for SARS-CoV-2 should be performed. If this is identified during the TC with the participant, an Unscheduled visit should be arranged.

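### Table 1's mandatory stop after moderate immediate hypersensitivity is not carried into the dose-eligibility criteria that sites work from (Protocol Sections 5.1.5 and 5.2.2)

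*Protocol*

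**What the plan says.** Table 1 in Protocol Section 2.8.1 lists the rule as a risk-minimization measure. It applies to anaphylaxis, or to immediate hypersensitivity within 4 hours, "of at least moderate severity following the administration of the study vaccine, subsequent doses of study vaccine will not be administered".

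Section 5.1.5 lists the reasons for withholding further study vaccine. Its only allergy item is "Development of new severe allergy to vaccine components since study enrollment". Its last item is general: a condition or examination finding for which, "in the opinion of the investigator, further study vaccine administration would not be in the best interest of the participant".

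Section 5.2.2 imports that list for every later dose: "A participant may not receive additional study vaccine administrations for any of the reasons outlined in Section" 5.1.5. It then adds participant request, loss to follow-up, new safety information and termination of study vaccinations. It adds no hypersensitivity item.

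Sites are directed to Section 5.1.5 in three other places:
- Section 4.4, at the Day 92 visit: "participants will be evaluated by the Investigator according to Further Study Vaccine eligibility criteria".
- Section 6.1: confirmation of "eligibility to receive additional study vaccine must be entered into the IRT prior to dispensing the assigned vaccination on Day 92".
- Appendix 1, Day 92 to end-of-study schedule, footnote i: "Study vaccine will be administered in an observer-blind fashion at Day 92 and Day 120 (if the participant meets eligibility criteria for" further vaccine).

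**The concern.** A safety stop works only if it is in front of the person deciding on the next dose. Here the stop sits in an introductory risk table, while the list that investigators are told to apply carries a different threshold. A site working through Sections 5.1.5 and 5.2.2 could miss the Table 1 rule and give a dose that Table 1 prohibits, or two sites could handle the same reaction differently. What is at stake is participant safety and consistent conduct. No estimate or error rate is involved.

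**Working it through.** No arithmetic applies. The check takes one event, a moderate, non-anaphylactic hypersensitivity reaction within 4 hours of a study dose, and follows it through the protocol.

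| Protocol text | What it does with this event |
|---|---|
| Table 1 (2.8.1) | Stops all later study doses; mandatory |
| 4.5.3.2 | Acts only on a severe immediate event, by observation and a call to the CRO medical monitor; silent on later doses |
| 5.2.1 (delay criteria) | No hypersensitivity item |
| 5.1.5 allergy item | Requires a severe allergy; no 4-hour window |
| 5.1.5 last item | May withhold, at the investigator's discretion; no grade stated |
| 5.2.2 added reasons | No hypersensitivity item; new safety information might be read to cover it |
| 5.1.2, exclusion 5 | Broader (a past anaphylactic, urticarial or otherwise significant reaction to the vaccine), but an entry criterion; Appendix 1 schedules that review at Screening only |

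Only Table 1 stops this participant by an explicit rule.

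**Do the thresholds differ?** Section 7.4.1.2.1 separates the grades: "The intensity of unsolicited AEs will be rated as mild, moderate, or severe using the following criteria". A moderate event is therefore not a severe one on the protocol's scale for unsolicited events. The protocol does not tie the 5.1.5 allergy item to that scale, so the comparison rests on the ordinary reading of the two terms.

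**When is Section 5.1.5 applied?** The formal review is at Day 92 in Phases 1, 2, 3a and 3b (Sections 4.4, 5.1.5 and 6.1, and the eligibility row in Appendix 1). Footnote i mentions Day 120. Day 29, and Phase 3c altogether, are reached only through Section 5.2.2.

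**Where can active vaccine be given again?** From Sections 4.4 and 4.5.2:

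| Participants | Day 29 | Day 92 | Day 120 |
|---|---|---|---|
| Phase 1/3b, ARCT-154 first | Repeat ARCT-154 | Saline | Saline |
| Phase 2/3a, ARCT-154 first | Repeat ARCT-154 | Repeat ARCT-154 or saline (3:1) | Saline |
| Phase 1/2/3a/3b, placebo first | Saline | First ARCT-154 | Repeat ARCT-154 |
| Phase 3c | Repeat ARCT-154 or ChAdOx1 | None | None |

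The doses that matter most are therefore Day 29 in all phases, Day 92 for Phase 2/3a participants re-randomized to ARCT-154, and Day 120 for placebo-first participants. Only the Day 92 group falls squarely under the formal review.

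**Can the rule be applied with existing data?** Yes. Adverse events are reviewed at each dosing visit (4.5.3.2), and onset time is recorded for events within 24 hours of vaccination (7.4.1.3). Minimum observation is 3 hours for the initial Phase 1 doses and 15 or 30 minutes elsewhere (4.5.3.2, Appendix 1). Part of the 4-hour window therefore falls after discharge. Reactions in that part may come to light only by later report and must then be matched to a dosing rule.

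**The case against.** The strongest reply is that there is no conflict. Table 1 is protocol text in mandatory words, both rules can be followed together, and a rule stated once need not be repeated. A reader might infer from Section 5.1.5 that re-dosing after a moderate reaction is allowed. The documents do not support that: nothing in Section 5.1.5 or 5.2.2 permits it. What remains is a threshold missing from the list that sites must confirm.

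Second, the two items address different events. Table 1 concerns a reaction within 4 hours of a study dose. The 5.1.5 item covers severe component allergy arising at any time since enrollment, from any exposure. This stands, and it means the 5.1.5 item must be kept: replacing it with the Table 1 wording would drop severe allergy that is delayed or arises outside study dosing.

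Third, a reader might infer that the Day 92 gap exposes the roughly 16,000 Phase 3b participants to a repeat of the vaccine they reacted to. It does not. Those who started on ARCT-154 receive saline at Day 92 and Day 120, and those who started on placebo receive their first ARCT-154 dose at Day 92. This also stands.

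Fourth, there are other safeguards: the investigator-opinion item, a Section 5.2.2 list that is not plainly exhaustive, adverse-event review at dosing visits, and ongoing blinded review by the Safety Review Committee. They make oversight less likely, but none carries the moderate threshold. The IRT screens and Pharmacy Manual are not among the documents and may repeat the rule.

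Finally, Section 2.6 lists urticaria among the most common unsolicited events with the predecessor vaccine ARCT-021. It gives no rate, timing or grade, so it cannot be used to size the problem.

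**Conclusion.** The point holds as a mismatch in where and how a safety stop is stated. A moderate, non-anaphylactic immediate reaction is barred by Table 1 but matches no explicit criterion in Section 5.1.5 or 5.2.2. Because Table 1 still binds, the consequence is possible oversight or inconsistent application.

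The gap is narrow. The reaction must be moderate, not anaphylactic, not regarded as severe allergy, and not caught by investigator judgment. The number of participants affected is unknown, since neither document gives a rate for such reactions. No endpoint, power or alpha figure changes. The conclusion assumes the ordinary meaning of severe allergy and that no site tool outside these documents already carries the Table 1 rule. It is still worth fixing, because the rule is a participant-safety stop and aligning the text is cheap.

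**What to change.** Keep the severe-allergy item in Section 5.1.5. Add to Sections 5.1.5 and 5.2.2 one mandatory criterion that matches Table 1: no further study vaccine after anaphylaxis, or after immediate hypersensitivity (within 4 hours) of at least moderate severity, following any study dose. State that it is checked before the Day 29 dose in all phases including 3c, and before the Day 92 and Day 120 doses.

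The cost is a sentence in each of two sections, with no new data collection. A few more doses may be withheld, but Table 1 already requires that. Where dosing is complete, the recorded onset times and grades can be used to list any dose given after a reaction that Table 1 should have stopped.

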5.2 Delaying or Discontinuing Study Vaccination and Participant Withdrawal From the Study

5.2.1 Delay in Study Vaccination

Body temperature must be measured and the participant asked about recent concomitant medication/vaccine receipt prior to each administration of study vaccine.

The following events constitute criteria for delay of study vaccination and the window of delay specified forthwith:

- On planned Day 1, close contact with a person known to be SARS-CoV-2 positive or with a clinical diagnosis of COVID-19 within 7 days prior to enrollment.
 - Participants meeting this criterion who remain asymptomatic for 7 days may be rescheduled for vaccination.
- Acute moderate or severe infection with or without fever at the time of dosing (delay: until afebrile for 48 hours and clinically improved according to investigator judgment)
 - Participants with minor illness and without fever may be vaccinated if deemed appropriate according to investigator judgment.
- Fever without signs of acute illness, defined as body temperature 100.4°F ($\geq 38.0^{\circ}\text{C}$) (delay: until afebrile for 48 hours).
- Use of antipyretics or analgesics within 24 hours.
- Receipt of vaccines or specified steroid doses close to the time of intended study vaccination.
 - Vaccination will be deferred to confirm 28 days since receipt of a live replicating vaccine.

- Vaccination will be deferred to confirm 14 days since receipt of an inactivated or non-replicating vaccine.
- Vaccination will be deferred to confirm at least 28 days since receipt of systemic steroid therapy.
- Participants who are confirmed to be RT-PCR positive for SARS-CoV-2 after the first study vaccine administration, should still receive the second study vaccine administration if deemed appropriate by the Investigator. However, the second vaccine administration should be at least 28 days after the date of the positive RT-PCR result, and at the time of vaccination the participant must not meet any other criteria for delay in study vaccination (as outlined above).

Vaccination may be performed once these criteria are no longer met. For the first vaccination this will not constitute a protocol deviation as long as the vaccine is administered within 28 days after signing the informed consent. If greater than 28 days, then participants must be rescreened.

If vaccination is delayed for any of the reasons described above, subsequent study visits will be based on calendar days after the receipt of the study vaccine.

